## **8.4 Clinical Laboratory Tests (Serum Chemistry, Hematology, Coagulation and Urinalysis)**

Safety serum chemistry, hematology and urinalysis tests are performed at Screening, Day -8 check-in, Day 1 predose, Day 6 and Day 12. For anuric patients, urinalysis may not be performed. Platelet count are collected at start and end of HD on Days -7, -5, -3, 1, 3, 5 and 12 and on Day 6. Platelet count are collected at start and end of HD on Days -7, -5, -3, 1, 3, 5 and 12 and Day 6. aPTT results are presented and discussed in the PD Section 7.2.

Out-of-range values and clinically significant results will be listed.

For all numeric laboratory values, descriptive statistics will be presented for each laboratory test by assessment time point and treatment. Change from baseline will be summarized in a similar manner. Baseline is defined as the result closest and prior to

dose which may include unscheduled results. This will typically be the result collected at predose on Day 1. Postdose unscheduled events or early termination results will not be included in summaries.

For each laboratory test, a shift table will be developed to compare the frequency of the results at baseline (above normal, normal, or below normal) with the respective postdose results.

Coagulation parameters and platelet count will be listed and presented together since they have the same timepoints. Urinalysis test results will be listed only.

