- k: The dialysate sample will be taken at 30 minutes and at 3 hours after the start of hemodialysis. The dialysate will be freeze and sent to Aronora.
- l: To be performed when the dialyzer cartridge is removed and collected at the end of HD.
- m: To be performed prior to dosing.
- n: A single dose of xisomab 3G3 or matching placebo will be administered at Hour 0. The dose will be injected through a port into the flowing arterial blood in the proximal dialysis line according to the randomization schedule, immediately after the start of HD.
- o: When the PK or PD sample is on an HD day, the sample should be taken at least 1 hour prior the start of HD session. The actual time will be recorded.
- p: To be performed at discharge or early termination; the PK and aPTT should be taken at 120 hour postdose.
- q: The vascular access sites (AV fistula or AV graft puncture sites) are to be evaluated immediately after the end of HD and removal of the needles from the fistula or graft for bleeding cessation or other reactions.
- r: All patients who received the study drug or placebo (including patients who terminate the study early) will undergo follow-up procedures at the Clinical Research Unit (CRU) approximately 12 days after dosing, as they return for their last HD. Events performed on Day 12 can be performed at end of HD if more appropriate.
- s: Platelet count, BUN and potassium, and aPTT value will be taken from the hematology, serum chemistry, and coagulation sample, respectively, when these are scheduled to be collected at the same time. Samples will not be taken twice at a same timepoint.

Abbreviations: ♀ = Females, AE = Adverse events, BUN = Blood urea nitrogen, BP = Blood pressure, C-I = Check-in, Chem = Chemistry, ConMeds = Concomitant medication, CRU = Clinical research unit, ECG = Electrocardiogram, FSH = Follicle-stimulating hormone, FU = Follow-up, Hem = Hematology, HD = Hemodialysis, HIV = Human immunodeficiency virus, HR = Heart rate, Kt/V = ratio of volume of fluid completely cleared of urea, PD = Pharmacodynamic, PK = Pharmacokinetics, PMP = Postmenopausal, RR = Respiratory rate, T = Temperature, UA = Urinalysis, URR = Urea reduction ratio.

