11.3 Early Termination of Patients from the Study

Patient participation in this study may be discontinued for any of the following reasons:

1. Occurrence of any medical condition or circumstance that exposes the patient to substantial risk and/or does not allow the patient to adhere to the requirements of the protocol.
2. If the patient clots the hemodialyzer twice they may be discontinued from the study at the discretion of the PI. If the patient fully clots the hemodialyzer, continuation of the patient in the study will be at the PIs discretion.
3. Any SAE, clinically significant AE, severe laboratory abnormality, intercurrent illness, or other medical condition that indicates to the PI that continued participation is not in the best interest of the patient.
4. Patient's decision to withdraw.
5. Requirement of prohibited concomitant medication.
6. Patient failure to comply with protocol requirements or study related procedures.
7. Termination of the study by the Sponsor, FDA, Celerion, CRU, or other regulatory authorities.

The clinical report will include reason(s) for patient withdrawals as well as details relevant to the patient withdrawal.

If a patient is withdrawn from the trial prior to study completion, the patient will undergo all procedures scheduled for early termination as the situation allows (see the Study Events Flow Chart ([Section 6](#))). Any patient withdrawn due to an AE (whether serious or non-serious) or clinically significant abnormal laboratory test values will be evaluated by the PI or a monitoring physician and will be treated and/or followed up until the symptoms or values return to normal or acceptable levels, as judged by the PI or designee.

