13.3 Hemodialysis Procedure and Blood Clots in the Dialyzer Cartridge

Patients will undergo hemodialysis 3 times a week as delineated in the Study Events Flow Chart ([Section 6](#)). For each patient, the hemodialysis will last at least 3 hours as per patient standard schedule which will be the same throughout the study.

Patients undergoing heparin-free hemodialysis may be at higher risk of developing clots within the hemodialysis circuit. In order to monitor clotting within the HD circuit, venous pressure will be continuously monitored. Should clotting within the dialyzer occur, site standard operating procedures will be followed to replace the clotted dialyzer and resume hemodialysis under the supervision of the PI, if appropriate. It is important to note that replacement of the dialyzer cartridge is a safe procedure for the patient. While studies

suggest that there is no risk of thromboembolic complications should this occur, clotting of the dialyzer circuit could result in up to ~228 mL of blood loss.

The hemoglobin levels will be followed more closely.

If the patient clots the hemodialyzer twice they may be discontinued from the study at the discretion of the PI. If the patient fully clots the hemodialyzer, the continuation of the patient in the study will be at the PIs discretion.

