### **8.5 Vital Signs**

Vital signs tests (HR, BP, RR and T) will be assessed at Screening, Day -8 check-in, start of HD on Days -7, -5, -3, 1, 3, 5, 8, 10 and 12, 1 hour postdose on Day1, Day 6 discharge or early term and Day 12 follow-up.

Vital sign results will be summarized by dose level, pooled placebo, and time point. Change from baseline will be summarized in a similar way. Baseline is defined as the result closest and prior to the dose on Day 1, which may include unscheduled results, whichever is later. Postdose unscheduled events or early termination results will not be included in summaries.

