### **8.6 Electrocardiogram**

Safety ECGs (HR, PR, QRS, QT and Fridericia correction QTcF) will be assessed at Screening, Day -8 check-in, Day 1 predose, Day 6 (discharge or early term) and Day 12 follow-up.

ECG parameters will be summarized by dose level, pooled placebo, and time point. Change from baseline will be summarized in a similar way. Baseline is defined as the result closest and prior to the dose on Day 1, which may include unscheduled results, whichever is later. Postdose unscheduled events or early termination results will not be included in summaries.

The QTcF values that are  $> 450$  ms and increase from baseline  $> 30$  ms, will be flagged in the data listings.

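### By-arm laboratory, vital-sign and ECG summaries leave out post-dose unscheduled and early-termination results, so the comparison with placebo can miss the most extreme values

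*SAP*

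**What the plan says.** SAP 2.2 makes changes in laboratory values, vital signs and ECGs part of the primary outcome, judged against pre-treatment and placebo.

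SAP 8.4, 8.5 and 8.6 then apply one rule to all three data types: "Postdose unscheduled events or early termination results will not be included in summaries". Unscheduled results are allowed before dosing. For vital signs, "Baseline is defined as the result closest and prior to the dose on Day 1, which may include unscheduled results, whichever is later"; the ECG and laboratory sections are equivalent.

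Sections 8.5 and 8.6 also name early termination as part of a planned assessment: "Day 6 discharge or early term and Day 12 follow-up" for vital signs and "Day 6 (discharge or early term) and Day 12 follow-up" for ECGs. The protocol flow chart does the same in footnote p, which covers Day 6 laboratory tests as well: "To be performed at discharge or early termination; the PK and aPTT should be taken at 120 hour postdose".

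The protocol foresees results of the excluded kind:

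- Sections 13.2.2, 13.2.3 and 13.2.7 allow extra vital signs, ECGs and laboratory tests at any time.
- Section 11.3 lists among the withdrawal reasons an SAE, a clinically significant AE, or a "severe laboratory abnormality, intercurrent illness, or other medical condition that indicates to the PI" that staying in the study is not in the patient's interest. It also calls for early-termination procedures.
- Section 13.3, on circuit clotting with possible blood loss of up to about 228 mL, says "The hemoglobin levels will be followed more closely" but gives no time points.

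For display, SAP Section 8 lists all CRF data by patient, including rechecks, unscheduled and early-termination results. The shell for Tables 14.3.4.1 to 14.3.4.3 (out-of-range and clinically significant laboratory results) tells the programmer to sort such results in by date.

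**The concern.** The values most likely to matter for safety in a small single-dose study are often taken off schedule: a recheck after an alarming result, a draw when a patient stops, a hemoglobin check after a clotted dialyzer. Under the SAP rule none of these enters the tables that set each dose beside pooled placebo.

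A patient withdrawn before Day 6 would have no Day 6 row in those tables. A patient whose hemoglobin fell between scheduled draws would appear only through whatever the next scheduled draw showed. With so few patients per arm, one such value can change the minimum, the maximum or a shift count.

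**Working it through.** The plan gives no figure on this point to reproduce. The check has two parts: tracing where each kind of result goes, and a rough count of how often the hemoglobin case might arise.

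**Where each result goes**

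1. Scheduled post-dose draws. SAP 8.4 schedules post-dose hematology and chemistry on Days 6 and 12 only. The extra dialysis-day samples give platelet counts and coagulation, not hemoglobin. SAP 8.6 schedules post-dose ECGs on Days 6 and 12 only. Vital signs are denser, at 1 hour post-dose and at each dialysis.
2. A hemoglobin check prompted by clotting on Day 1, 3, 5, 8 or 10 is therefore unscheduled and excluded. On Day 12 hematology is scheduled.
3. Take a patient who withdraws on Day 3 with an abnormal early-termination draw. That draw is excluded. No Day 6 value exists unless the early-termination draw is counted there, which the SAP leaves unclear. The Day 6 denominator falls from 6 to 5, or from 8 to 7. The Day 12 follow-up required by Protocol 10.1.1 is summarized.
4. Displays for excluded results:

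| Data | By-arm summary and change from baseline | By-arm shift table | By-patient display |
|---|---|---|---|
| Laboratory | Excluded (14.3.5.1, .3, .5) | Excluded on the natural reading (14.3.5.2, .4, .6) | Tables 14.3.4.1 to 14.3.4.3 if abnormal; Appendix 16.2.8.1 |
| Vital signs | Excluded (14.3.5.7) | None planned | Appendix 16.2.8.2 only |
| ECG | Excluded (14.3.5.8) | None planned | Appendix 16.2.8.3 only, with QTcF flags |

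5. The shift-table entry is a reading, not a certainty. The shift sentence in 8.4 comes after the exclusion and speaks of the matching post-dose results. The shell has one row per time point, but SAP Section 11 says shells may not show every aspect of the study.

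**Size**

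1. Arm sizes: 2:1 allocation in cohorts of 9 to 12 gives 9 × 2/3 = 6 to 12 × 2/3 = 8 patients per dose. Placebo is 3 to 4 per cohort, so 6 to 8 pooled. One patient is 1/8 = 12.5% to 1/6 = 16.7% of an arm.
2. Exchange rate: Protocol 8.4.1 gives cartridge exchange in 5-7% of heparin-free procedures.
3. Affected sessions: Days 1, 3, 5, 8 and 10, that is five.
4. Probability of at least one exchange per patient is 1 − (1 − p)^5:
   - p = 0.05: 1 − 0.95^5 = 1 − 0.7738 = 22.6%
   - p = 0.07: 1 − 0.93^5 = 1 − 0.6957 = 30.4%
5. Expected patients per arm: 6 × 0.226 = 1.4 to 8 × 0.304 = 2.4.

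This assumes independent sessions and no drug effect. It counts exchanges, not hemoglobin draws. Clustering of clotting within patients, a working drug, or discontinuation after repeated clotting would all lower it.

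**The case against.** The strongest reply is that nothing is hidden. Abnormal off-schedule laboratory values appear in Section 14 with dose level, high/low flags and clinical significance. SAP 8.1 tabulates withdrawals by arm and reason. Protocol 13.2.8.1 lets an abnormal laboratory finding be an AE, and TEAEs are tabulated by arm, severity and relationship. Protocol 8.4.1 describes the primary endpoint as the number of adverse events. Protocol 14.3.1 plans summaries by time of collection, and unscheduled values share no common time. With up to 24 patients and no hypothesis test, a reader can go through individual values.

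Most of this stands, and it defeats several stronger readings that a reader might reach:

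- **That these results vanish from the safety tables.** They do not; the loss is confined to the by-arm numerical summaries and, probably, the shifts.
- **That the drug will look safer than it is.** The rule is the same in every arm. Protocol 8.4.1 expects the drug to reduce clotting; if it does, omitted hemoglobin falls would lie mainly in the placebo group and the rule would hide a benefit. Nor do the documents say that a fall would have recovered by the next scheduled draw.
- **That an unscheduled pre-dose baseline is part of the fault.** Taking the last pre-dose value is a coherent definition and omits no post-dose result.
- **That all six sessions from Day 1 to Day 12 are affected.** Day 12 has scheduled hematology, and a Day 5 fall is followed by the scheduled Day 6 draw.

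The reply does not supply a by-arm view of magnitude. Tables 14.3.4.1 to 14.3.4.3 are per-patient displays, AE tables depend on the investigator's judgement and give counts, and off-schedule vital signs and ECGs have no Section 14 table of their own. Keeping by-visit means on scheduled data is sound, but it does not prevent an added worst-value summary.

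**Conclusion.** The point holds as a limited gap in by-arm reporting. Under SAP 8.4 to 8.6, the arm-level descriptive and change-from-baseline tables cannot show an extreme value from an unscheduled or early-termination assessment. On the natural reading the shift tables cannot either. The gap is widest for vital signs and ECGs. No direction of bias can be claimed.

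One affected patient is 12.5% to 16.7% of an arm. The 22.6% to 30.4% of patients with at least one exchange is a rough upper guide to how often the hemoglobin case could arise. It rests on the protocol's 5-7% rate, independent sessions, no drug effect, and every exchange leading to a draw, which Protocol 13.3 does not say.

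Separately, 8.5 and 8.6 name early termination within the Day 6 assessment and then exclude early-termination results. As written, two programmers could build different Day 6 rows. The passages must be reconciled.

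**What to change.** In SAP 8.4, 8.5 and 8.6, replace the exclusion sentence with wording such as:

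> Unscheduled and early-termination post-dose results are not used in by-visit statistics. They are used, with scheduled results, to derive each patient's minimum and maximum post-dose value, the change of each from baseline, and, for laboratory tests, the shift from baseline to worst post-dose category in each direction.

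Then:

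- Add the minimum and maximum post-dose value and their changes from baseline, by arm, to Tables 14.3.5.1, 14.3.5.3, 14.3.5.5, 14.3.5.7 and 14.3.5.8.
- Add a baseline-to-worst-post-dose shift, by arm, to Tables 14.3.5.2, 14.3.5.4 and 14.3.5.6.
- In Table 14.3.5.5, state which baseline the new row uses, because the shell note for PT and INR takes the same-day pre-dialysis value as baseline.
- In 8.5 and 8.6, and for laboratory tests in 8.4, state whether an early-termination result counts at the Day 6 time point.

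The cost is SAP wording and a few extra rows per parameter, using data already collected. The downside is that a patient with more rechecks has more chances to show an extreme value, so the by-visit summaries should stay alongside.

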### **8.5 Vital Signs**

Vital signs tests (HR, BP, RR and T) will be assessed at Screening, Day -8 check-in, start of HD on Days -7, -5, -3, 1, 3, 5, 8, 10 and 12, 1 hour postdose on Day1, Day 6 discharge or early term and Day 12 follow-up.

Vital sign results will be summarized by dose level, pooled placebo, and time point. Change from baseline will be summarized in a similar way. Baseline is defined as the result closest and prior to the dose on Day 1, which may include unscheduled results, whichever is later. Postdose unscheduled events or early termination results will not be included in summaries.

### **8.6 Electrocardiogram**

Safety ECGs (HR, PR, QRS, QT and Fridericia correction QTcF) will be assessed at Screening, Day -8 check-in, Day 1 predose, Day 6 (discharge or early term) and Day 12 follow-up.

ECG parameters will be summarized by dose level, pooled placebo, and time point. Change from baseline will be summarized in a similar way. Baseline is defined as the result closest and prior to the dose on Day 1, which may include unscheduled results, whichever is later. Postdose unscheduled events or early termination results will not be included in summaries.

The QTcF values that are  $> 450$  ms and increase from baseline  $> 30$  ms, will be flagged in the data listings.

### **8.7 Concomitant Medications**

All concomitant medications recorded during the study will be coded with the WHO Dictionary Version September 2018, B3 and listed.

### **8.8 Physical Examination**

Full physical examinations will be performed at Screening and Day -8 check-in and abbreviated physical examination will be performed on Days 1, 6 and 12. Abnormal findings will be reported as medical history or adverse events. All data found in the CRF will be listed.

### **8.9 Vascular Access Site Reaction**

Vascular access site reaction will be assessed at predose on Day 1 and end of HD on Days 1, 3 and 5. Any new abnormal findings inconsistent with past skin injuries as expected in patient on chronic HD will be reported as AEs.

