| Safety Evaluations | | | | | | | | | | | | | | | | | | | | |
| Abbreviated Physical Examination ^{e:} | X ^{m:} | | | | | | | | | | | | | | | | | | X ^{p:} | |
| Weight | X ^{f:} | | | | | X ^{g:} | | | | | | X | | X ^{f:} | X ^{g:} | X | | X ^{f:} | X ^{g:} | X ^{p:} |
| 12-Lead Safety ECG | X ^{m:} | | | | | | | | | | | | | | | | | | X ^{p:} | |
| Vital Signs (HR, BP, RR and T) | X ^{m:} | | | X | | | | | | | | | X ^{f:} | | | | X ^{f:} | | X ^{p:} | |
| Bleeding of Access Site | | | | | | X ^{g:} | | | | | | | | | X ^{g:} | | | X ^{g:} | | |
| Hem, Serum Chem ^{h:} , and UA ^{i:} | X ^{m:} | | | | | | | | | | | | | | | | | | X ^{p:} | |
| Coagulation ^{j:} | X ^{f:} | | | | | X ^{g:} | | | | | | | X ^{f:} | X ^{g:} | | | X ^{f:} | X ^{g:} | X ^{p:} | |
| Platelet Count ^{s:} | X ^{f:} | | | | | X ^{g:} | | | | | | | X ^{f:} | X ^{g:} | | | X ^{f:} | X ^{g:} | | |
| AE Monitoring | | | | | | | | | | | | | X | | | | | | | |
| ConMeds Monitoring | | | | | | | | | | | | | X | | | | | | | |
| Study Drug Administration / PK/PD/Immunogenicity | | | | | | | | | | | | | | | | | | | | |
| Xisomab 3G3 Administration ^{n:} | X | | | | | | | | | | | | | | | | | | | |
| Blood for free xisomab 3G3 PK | X ^{o:} | X | X | X | X | X | X | X | X | X | X | X | X ^{o:} | | | X ^{o:} | | X ^{p:} | | |
| Blood for free xisomab 3G3 PD (aPTT) ^{s:} | X ^{o:} | X | X | X | X | X | X | X | X | X | X | X | X ^{o:} | | | X ^{o:} | | X ^{p:} | | |
| Blood for Immunogenicity | X ^{m:} | | | | | | | | | | | | | | | | | | | |
| Blood BUN and Potassium (for Kt/V and URR) ^{s:} | X ^{f:} | | | | | X ^{g:} | | | | | | | X ^{f:} | X ^{g:} | | | X ^{f:} | X ^{g:} | | |
| Dialysate Analysis | | | X ^{k:} | | | X ^{k:} | | | | | | | X ^{k:} | X ^{k:} | | | | | | |
| Visual Assessment and Processing of Dialyzer Membrane | | | | | | X ^{l:} | | | | | | | X ^{l:} | | | | X ^{l:} | | | |
| Other Procedures | | | | | | | | | | | | | | | | | | | | |
| Vascular Access Site Reaction | X ^{m:} | | | | | X ^{q:} | | | | | | | X ^{q:} | | | | X ^{q:} | | | |
| Confinement in the CRU | | | | | | | | | | | | | X | | | | | | | |
| Return Visit | | | | | | | | | | | | | | | | | | | | |

| Study Procedures ^{a:} | Study Days | | | | | | |
|---|------------------|-----------------|------------------|-----------------|------------------|-----------------|------------------|
| | Follow-up Period | | | | | | |
| | Days → | 7 | 8 | 9 | 10 | 11 | 12 |
| | HD → | | HD ^{d:} | | HD ^{d:} | | HD ^{d:} |

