9.2 Endpoints

Primary outcome measures:

- The safety and tolerability of xisomab 3G3 will be evaluated versus pre-treatment and placebo by reviewing number and severity of adverse events and use of concomitant medications, physical examination, vascular access site reaction, bleeding time, and changes in vital signs, ECGs, and clinical laboratory evaluations.

Secondary outcome measures:

- PD using dose-dependency of drug potency, determined by measuring changes in coagulation parameters, and thrombus accumulation (assessed and ranked by visual inspection) within the dialyzer cartridges and total protein accumulation in the HD filter after xisomab 3G3-treatment versus pre-treatment and placebo.
- Efficacy on hemodialysis efficiency using BUN and potassium levels before and after hemodialysis, length of HD, measurement of urea removed by 3 hours of dialysis, and total dialysate urea (single pool Kt/V and URR) after xisomab 3G3-treatment versus pre-treatment and placebo.

Other outcome measures:

- PK parameters of xisomab 3G3, calculated, as appropriate: AUC0-t, AUC0-inf, AUC%extrap, Cmax, Tmax, Kel, t^{1/2}, CL, and Vss.
- Development of immunity or antibodies against xisomab 3G3 after drug exposure.

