10 STUDY DESIGN

10.1 Overall Study Design and Plan

This is a phase 2, randomized, double-blind, placebo-controlled, single-dose study of xisomab 3G3 designed to evaluate the safety, efficacy/potency, and PK at 2 dose levels administered to patients with ESRD undergoing HD.

A total of up to 24 adult male and female patients will be enrolled; 9-12 patients are planned for each cohort. In each cohort, an attempt will be made to enroll at least 50% of females and at least 30% of a race/ethnicity minority group. Patients will be enrolled into Cohort 1 or Cohort 2; cohorts will be dosed sequentially. Within a cohort, patients will be randomized to active drug or placebo as summarized below:

Table 2: Cohort and Treatment Randomization

| Cohort | Treatment | Active:Placebo | Cohort Size |
|--------|--|----------------|-------------|
| 1 | Infusion dose of 0.25 mg/kg xisomab 3G3 or placebo | 2:1 | 9-12 |
| 2 | Infusion dose of 0.5 mg/kg xisomab 3G3 or placebo | 2:1 | 9-12 |

This study includes a screening period of 28 days prior to checking-in to the clinical research unit on Day -8. From Day -7 (one week prior to dosing on Day 1) through Day -1, all patients will undergo HD 3 times and will be assessed for all scheduled procedures and endpoints before and after each HD session as per the Study Events Flow Chart ([Section 6](#)).

On Study Day 1, prior to dosing, patients will undergo baseline measurements followed by initiation of a regular HD procedure, consistently using only one type of dialyzer cartridge in each patient. Immediately after the start of blood perfusion, a single dose of xisomab 3G3 or matching placebo will be injected through a port into the flowing arterial blood in the proximal dialysis line. Patients will continue to undergo HD procedures and scheduled assessments from Day 1 through Day 12.

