### 2.2 Endpoints

#### Primary outcome measures:

- The safety and tolerability of xisomab 3G3 will be evaluated versus pre-treatment and placebo by reviewing number and severity of adverse events and use of concomitant medications, physical examination, vascular access site reaction, bleeding time, and changes in vital signs, ECGs, and clinical laboratory evaluations.

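### Access site reaction has no post-dialysis grade before dosing, so its comparison with pre-treatment cannot separate the dialysis session from the drug

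*SAP*

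**What the plan says.** **Status of the measure.** Protocol 9.2 sets out how safety and tolerability are judged: "evaluated versus pre-treatment and placebo by reviewing number and severity of adverse events and use of concomitant medications, physical examination, vascular access site reaction". The same list then adds bleeding time, vital signs, ECGs and laboratory tests. SAP 2.2 repeats both comparators. Site reaction and bleeding time are separate components.

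**Schedule.** SAP 8.9 reads: "Vascular access site reaction will be assessed at predose on Day 1 and end of HD on Days 1, 3 and 5". The Protocol Section 6 flow chart agrees. Its site-reaction row appears only in the PK/PD table; the evaluation-period and follow-up tables have no such row. The Day 1 predose entry carries footnote m ("m: To be performed prior to dosing"). The later entries carry footnote q, which places the look straight after the session ends and the needles come out, and covers bleeding as well as other reactions.

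**Grading.** Protocol 13.2.5 grades pain, tenderness, erythema and induration. New findings that do not fit past access injuries are to be reported as adverse events. It also describes a pre-session look at the site for inflammation, infection or flow problems, without naming days or a grade.

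**Run-in.** Protocol 10.1 says of the week before dosing: "all patients will undergo HD 3 times and will be assessed for all scheduled procedures and endpoints before and after each HD session". The flow chart is named there as the governing schedule. Protocol 8.4.1 gives the purpose of this period as a baseline for heparin-free dialysis.

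**Analysis.** Protocol 14.3.1 promises a summary of site reaction by treatment and collection time. SAP 8.9 specifies no summary, and the output lists in SAP 10.1 to 10.3 name no site-reaction table or listing. SAP 8 has only its general commitment to list all CRF data.

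**The concern.** A comparison with pre-treatment is informative when the two assessments differ only in treatment. Here they differ in two respects. The Day 1 predose look comes before dosing; every later look comes straight after a session of at least 3 hours (about 4 by SAP 9) and the removal of the needles. Pain, tenderness, redness and swelling at a puncture site are signs that cannulation can plausibly produce. If a grade rises from predose to post-session, the patient's own data cannot say whether the session or the drug was responsible.

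The stake is one of the two comparisons named for a primary component. A patient's own post-session values would be useful in a study this small, because patients may differ in access type (fistula or graft) and cannulation technique (ladder or buttonhole). The run-in was designed to provide a procedural baseline, and for this component it yields no scheduled grade.

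**Working it through.** The plan gives no figure to reproduce: Protocol 14.1 says that the sample size was chosen without statistical considerations. The check is a count of scheduled assessments.

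**Inputs**
- Dialysis sessions (flow chart footnote d): Days -7, -5 and -3 before dosing (3); Days 1, 3, 5, 8, 10 and 12 from dosing onward (6).
- Site reaction: SAP 8.9 and the flow chart.
- Bleeding time: SAP 8.10 and Protocol 10.1, on Days -7, -5, -3, 1, 3, 5 and 12.
- Cohorts: two, of 9 to 12 patients each, randomized 2:1 (Protocol Table 2).

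**Scheduled assessments per patient**

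| | Site reaction | Bleeding time |
|---|---|---|
| Post-session, run-in | 0 of 3 | 3 of 3 |
| Predose, Day 1 | 1 | 0 |
| Post-session, from dosing onward | 3 of 6 (Days 1, 3, 5) | 4 of 6 (Days 1, 3, 5, 12) |

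Pre-treatment assessments that match the post-dose condition: 0 for site reaction, 3 for bleeding time. SAP 8.9 states the days in prose, so the gap is not an effect of how the flow chart was read from PDF.

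**What remains as a like-for-like reference**
- Placebo patients per cohort: 9/3 = 3 to 12/3 = 4.
- Pooled over two cohorts: 2 × 3 = 6 to 2 × 4 = 8.
- Their post-session grades on Days 1, 3 and 5: 6 × 3 = 18 to 8 × 3 = 24.

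**What the change would add**
- Total patients: 2 × 9 = 18 to 2 × 12 = 24.
- Run-in post-session grades: 18 × 3 = 54 to 24 × 3 = 72, against 0 now.
- Day 12 grades: 18 to 24, against 0 now.

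These are counts of observations. They do not estimate a bias or a gain in precision; the documents give no rate of procedure-related reactions from which to do so.

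**Other routes to run-in information**
- Adverse events are monitored from check-in (Protocol 13.2.8.2), with particular attention to the access site (13.2.5). This is event reporting without a scheduled grade, and SAP 8.3 summarizes only treatment-emergent events.
- The pre-session look in Protocol 13.2.5, even if made at every session, is not a post-session look.
- Bleeding cessation, which footnote q also mentions, does have run-in values through bleeding time. The gap concerns the four local-reaction signs.

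**The case against.** The strongest reply is that randomization already deals with needling. Both arms are assessed at the same post-session moments on Days 1, 3 and 5, so the contrast with placebo is fair. The study is descriptive, and SAP 8.9 defines no change from baseline for this measure, so no confounded statistic is actually specified. This stands, and it limits the point to the pre-treatment half of the stated comparison. It does not remove it: both documents name that half, and the schedule cannot support it.

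A reader might infer more than the documents show:

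- *That dialysis-related signs will appear as a change in every patient.* Not supported. Entry requires an established access with skin consistent with chronic use, erythema and induration grades start at 2.5 cm, and only new findings are reported as adverse events. Some session effects may be graded; how many is unknown.
- *That the run-in contributes nothing on the access site, or that nothing is seen on Day 12.* Too strong. Adverse events are recorded from Day -8, bleeding time is measured on those days, and Day 12 includes adverse event monitoring and an abbreviated physical examination. What is missing is the scheduled grade.
- *That Protocol 10.1 is contradicted.* Its sentence covers scheduled items and defers to the flow chart, which schedules no run-in reaction grade.
- *That every post-dose grade follows at least 10 minutes of manual pressure.* The text does not fix the order. Footnote q puts the assessment immediately after needle removal, Protocol 13.2.5 allows about 20 minutes after the session, and 13.2.6 describes the pressure separately.

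**Conclusion.** The point holds in this limited form. Site reaction is to be evaluated against pre-treatment and placebo, but there are 0 post-session pre-treatment assessments per patient against 3 post-session assessments after dosing. The comparison with pre-treatment therefore confounds the session with the drug. The placebo comparison, with 6 to 8 pooled patients, is intact, so the primary safety assessment does not fail.

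The conclusion rests on two things: that the flow chart and SAP 8.9 are the full schedule for this measure, and that a session with needle removal can plausibly affect the graded signs. It does not depend on how often that happens. It should be corrected because the run-in slot already exists and the present schedule cannot deliver a comparison named in the primary outcome.

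**What to change.** 1. In the flow chart and SAP 8.9, add the footnote-q assessment at the end of dialysis on Days -7, -5, -3 and 12, alongside the access-site bleeding check already scheduled on those days.
2. Define one pre-treatment reference in the SAP: for example, the worst post-session run-in grade for each sign, with the Day -3 grade as a sensitivity check. If the worst of three is used, compare it with the worst of Days 1, 3 and 5, so that both sides rest on three looks. Day 12 is a single look and is better set against the Day -3 grade.
3. Add a SAP table of grades for each sign by treatment (two dose levels and pooled placebo) and time point. This delivers the summary promised in Protocol 14.3.1; without it the added grades would have no planned display.

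The cost is a short inspection and a CRF line at four existing sessions, by staff already checking the same site, plus a flow chart amendment and a few lines in the SAP. No visit or blood sample is added.

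If the run-in is already complete, the grades cannot be recovered. In that case, say in the SAP and the study report that this component is compared with placebo only, and still add the table.
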